### 7.2.3 90-day Safety Follow-up Period

All patients must have safety evaluations 90 days after the last dose of study treatment. Information related to all AEs (including concomitant medication taken for ongoing AEs) will be collected for 90 days after the last dose of study drug. All AEs suspected to be related to study treatment should be followed up weekly or as clinically indicated until resolution or stabilization.

### 7.2.4 Survival Follow-up Period

Upon completion of the 90-day follow-up, patients will be followed for survival every 3 months (can be done by telephone call) until death or until the end of the study is reached, unless they withdraw consent or are lost to follow-up.

### 7.2.5 Lost to Follow-up

For patients whose status is unclear because they fail to appear for study visits without stating an intention to withdraw consent, the investigator should show "due diligence" by contacting the patient, family, or family physician as agreed in the informed consent and by documenting in the source documents steps taken to contact the patient, eg, dates of telephone calls, registered letters, etc, a patient should not be considered lost to follow-up until due diligence has been completed. Patients lost to follow-up should be recorded as such on the appropriate Patient Disposition eCRF.

## 7.3 Safety and Tolerability Assessments

Safety will be monitored by assessing physical examination, vital signs, body height and weight, hematology, chemistry, pregnancy, ECG, cytokine testing, as well as collecting of the AEs at every visit. For details on AE collection and reporting, refer to [Section 8](#), Adverse Events and Safety Reporting.

### 7.3.1 Physical Examination

Physical examination will be performed according to [Table 7-1](#).

At Screening (or RC1D1), prior to IMCgp100 infusion on the rollover study, a complete physical examination will be performed and will include the examination of general appearance, skin, neck (including thyroid), eyes, ears, nose, throat, lungs, heart, abdomen, back, lymph nodes, extremities, and neurological system. If indicated based on medical history and/or symptoms, rectal, external genitalia, breast, and pelvic exams will be performed.

From RC1D8 onwards, a short physical examination will be performed as indicated in the Schedule of Events, [Table 7-1](#). A short physical exam will include the examination of general appearance, vital signs (body temperature, pulse rate, respiratory rate, and blood pressure) and body sites as directed by symptoms.

Significant findings that were present prior to the signature of the informed consent must be included in the Medical History eCRF page. Significant new findings that begin or worsen after informed consent must be recorded on the AE eCRF page.

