**Table 7-3 Local Clinical Laboratory Parameters Collection Plan**

Test Category	Test Name
Hematology	Hematocrit, hemoglobin, platelets, white blood cells with differential (basophils, eosinophils, lymphocytes, monocytes, neutrophils)
Chemistry	Albumin, alkaline phosphatase, alanine transaminase, aspartate transaminase, bicarbonate, calcium, chloride, creatinine, glucose magnesium, inorganic phosphate, potassium, sodium, total bilirubin (also measure direct and indirect bilirubin if total bilirubin is > grade 1), blood urea nitrogen or urea, amylase, and lipase
Cytokines	

**Hematology:** The panels outlined in [Table 7-3](#) will be performed as per the assessment schedule in [Table 7-1](#).

**Clinical chemistry:** The panels outlined in [Table 7-3](#) will be performed as per the assessment schedule in [Table 7-1](#).

**Cytokine analysis panel:** The cytokine panel outlined in [Table 7-3](#) will be performed on an as needed basis in case a patient has an AE suspected to include cytokine release syndrome. This assessment should be performed at the following time points:

- [REDACTED]
- [REDACTED]

**Pregnancy and assessment of fertility:** Pregnancy tests will be performed for women of child bearing potential. At Screening, a serum pregnancy test must be performed within 72 hours before the first dose of IMCgp100. During the study (Day 1 of each cycle starting with Cycle 2), a serum or urine pregnancy test must be performed. At EOT, a serum or urine pregnancy test must also be performed. Pregnancy will be reported through the Pregnancy Reporting Form (paper) as well as in the eCRF as an AE.

**Cardiac assessments:** A standard 12-lead ECG will be performed as per the assessment schedule in [Table 7-1](#). ECG assessment is performed at Screening prior to the first dose and at EOT assessment. Clinically significant abnormalities present at Screening should be reported on the Medical History eCRF page. New or worsened clinically significant findings occurring after informed consent must be recorded on the AE eCRF page.

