## 8 ADVERSE EVENTS AND SAFETY REPORTING

### 8.1 Assessment of Safety

All patients who receive any treatment with IMCgp100 will be considered evaluable for safety. All AEs, regardless of study drug relationship, will be collected through the 90-day Safety Follow-up Period. At the time of consent, if any patient has any ongoing AE(s) from the parent IMCgp100 study, the AE(s) will be captured on the eCRF page and the "Ongoing at Start of Study" must be answered "Yes". The start date recorded in the eCRF for the rollover study should be equal to the start date of the event as recorded in the parent study. Timely, accurate, and complete reporting and analysis of safety information from clinical studies are crucial for the protection of patients and is mandated by regulatory agencies worldwide. The Sponsor and CRO have established standard operating procedures in conformity with regulatory requirements worldwide to ensure appropriate reporting of all safety information. All clinical studies conducted by the Sponsor or its affiliates will be conducted in accordance with those procedures.

Individual AEs should be evaluated by the investigator and should be reported to the CRO/Sponsor for evaluation. This includes the evaluation of the event's seriousness and the causality between the investigational medicinal product(s) and/or concomitant therapy and the AE. The CRO/Sponsor is required to maintain detailed records of all AEs reported by the investigator(s) and to perform an evaluation with respect to seriousness, causality, and expectedness. On request of a competent authority in whose territory the clinical trial is being conducted, the Sponsor should submit detailed records of all AEs which are reported by the relevant investigators. Case report processing concerns evaluation of data in individual cases, identification of individual cases requiring specific handling, recognition and processing of alerts, and any other data processing of aggregated cases.

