## **9.5 Primary Analysis**

### **9.5.1 Variables**

The primary variable is the incidence of AEs.

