## **9.9 Sample Size Calculation**

No formal sample sizing will apply to this study.

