6.5. Statistical Tests

There will be no formal statistical hypotheses testing.

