10.1. Derivations

- Age (years) will be derived using the following SAS code:

$$\text{floor} \left(\frac{(\text{intck}('month', \&birth, \&date) - (\text{day}(\&date) < \text{day}(\&birth)))}{12} \right)$$
 - &birth= Date of birth

- &date = (Date of informed consent)
- Note: For countries where only the year of birth is provided due to privacy laws, impute birth month and day as June 15.
- Time since primary diagnosis (years) = (Date of informed consent – Date of Primary Diagnosis + 1) / 365.25
 - Note: Partial primary diagnosis dates are imputed using 15th day of month if only month/year present or July 02 if only year present.
- Best response on any prior anti-cancer therapy for metastatic disease = the “best” *best response* as derived from the *Prior Anti-Cancer Therapy (PAT)* eCRF page, considering all medications identified from the medical review. From best to worst, the following order will be used:
 - Complete Response
 - Partial Response
 - Stable Disease
 - Progressive Disease
 - Non-Evaluable
 - Not Applicable
- BMI (kg/m²) = weight (kg) / (height (cm) / 100)²

11. Surgical and Medical History

Medical History information will be listed only.

- Medical History will be coded using Medical Dictionary for Regulatory Activities (MedDRA) central coding dictionary, using the latest version of MedDRA available at the time of coding for the reporting period.
 - Medical History conditions are defined as those conditions beginning prior to screening which stop prior to or are ongoing at Screening.
 - Presented by System Organ Class (SOC) and Preferred Term (PT).

12. Concomitant Medications

Concomitant medications and significant non-drug therapies will be presented and coded using the World Health Organization drug dictionary (WHODD), using the latest version available at the time of coding for the reporting period.

Medications will be listed by Preferred Name (coded) and by Reported Term.

See [APPENDIX 2](#) for handling of partial dates for medications. In the case where it is not possible to define a medication as prior, concomitant, or post treatment, the medication will be classified by the worst case; i.e. concomitant. (Refer to Protocol Section 6.2)

- ‘Prior’ medications are medications which started and stopped prior to the first dose of study drug of the rollover study.
- ‘Concomitant’ medications are medications which:

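### A parent-study AE still ongoing at rollover consent falls under both the AE rule in Protocol 8.1 and the Medical History wording in Protocol 7.3.1 and SAP 11, so its capture, and in some cases its TEAE status, can differ by site.

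*Protocol*

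**What the plan says.** Protocol 8.1 has a rule made for a rollover study. For events already present when a patient joins, it says that "if any patient has any ongoing AE(s) from the parent IMCgp100 study, the AE(s) will be captured on the eCRF page"; the item 'Ongoing at Start of Study' is answered Yes, and the start date "should be equal to the start date of the event as recorded in the parent study". The AE page is implied by the flag and the start date but is not named.

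Protocol 7.3.1 has a general rule for physical examination: "Significant findings that were present prior to the signature of the informed consent must be included in the Medical History eCRF page". It then sends findings that begin or worsen after consent to the AE page. The cardiac paragraph of Protocol 7.3.4 does the same for ECGs: "Clinically significant abnormalities present at Screening should be reported on the Medical History eCRF page". SAP section 11 states: "Medical History conditions are defined as those conditions beginning prior to screening which stop prior to or are ongoing at Screening". Medical history is listed only, not summarized.

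On the analysis side, Protocol 9.5.1 states "The primary variable is the incidence of AEs", and SAP 15.1 summarizes only TEAEs. SAP 15.1 defines these as AEs that started or worsened between the first rollover dose and 90 days after the last. The AE page collects an initial and a most extreme grade, but not the date on which the grade changed. An AE that might have worsened inside the window is therefore treated as treatment-emergent. The note under the TEAE algorithm in SAP Appendix 2 instead sets the study drug start date to the first parent-study dose.

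**The concern.** In an ordinary trial, sending findings present at consent to Medical History is harmless, because they precede the study drug. Here every patient is already receiving IMCgp100. Protocol 5.1 keeps out only ongoing, serious related toxicities that would preclude further dosing, so tolerable on-drug toxicities can enter the study. For these, the 7.3.1 wording and the SAP 11 definition pull against 8.1. So does the AE definition in Protocol 8.1.1, which requires onset or worsening after consent.

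A site that follows 8.1 creates an AE record with a parent-study start date. A site that follows 7.3.1 creates a Medical History entry, and an AE record only if the finding later worsens. A site that follows both enters the event twice. At stake is whether drug toxicity is captured in the same way across sites in a study whose primary variable is AE incidence.

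**Working it through.** The plan gives no figure to reproduce: "No formal sample sizing will apply to this study" and "There will be no formal statistical hypotheses testing". The check applies the SAP's TEAE rules to each recording route.

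**Routes.** Route 1 (Protocol 8.1): one AE record with the parent-study start date and the grades over the life of the event. Route 2 (Protocol 7.3.1 and SAP 11): a Medical History entry, plus a new AE record dated at worsening if the event worsens after consent.

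**Rules.**
- SAP 15.1 main text: TEAE if the start date is from the first rollover dose to 90 days after the last dose, or if the event started earlier and its most extreme grade exceeds its initial grade.
- Appendix 2 as written: TEAE if the start date is on or after the first parent-study dose and no later than 90 days after the last dose. There is no worsening step.
- Appendix 2 with the first rollover dose put in place of the parent date, to see whether changing the date alone would be enough.

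**Events.** All three start during the parent study and are ongoing at rollover consent.
- A: grade 1 throughout.
- B: starts at grade 1, peaks at grade 3 in the parent study, is back to grade 1 at consent, and does not worsen in rollover.
- C: grade 1 at consent, worsens to grade 3 in rollover.

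**TEAE status, route 1 / route 2:**

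| Event | SAP 15.1 main text | Appendix 2 as written | Appendix 2 with rollover date |
|---|---|---|---|
| A | No / No | Yes / No | No / No |
| B | Yes / No | Yes / No | No / No |
| C | Yes / Yes | Yes / Yes | No / Yes |

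The result for B under SAP 15.1 assumes that the parent-study grades are carried into the rollover record. The result for C under SAP 15.1 assumes that the recorded initial grade is below the peak reached in rollover. Neither document says what the initial grade of a carried-over AE is.

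A and B appear in the AE listing by route 1 only. In C, both routes give an AE record, but with different start dates.

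Severity can also differ. Suppose an event starts at grade 1, peaks at grade 3 in the parent study, falls to 1 and rises to 2 in rollover. With parent grades carried over, route 1 can place it in the grade 3 or higher column; route 2 gives a new grade 2 event.

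**Scale.** SAP 15.1 counts a patient once per category, so the percentage with any TEAE moves only for patients who have no other TEAE. One such patient moves it by 100 × 1/N points. N is not stated; for assumed N of 5, 10 and 20 this is 20, 10 and 5 points.

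**The case against.** The strongest reply is that the protocol already shows which section governs. Section 7.3, which contains 7.3.1 and 7.3.4, refers to Section 8 for AE collection, and 8.1 has a specific rule and a dedicated eCRF item for this case. The rules also differ in scope: 8.1 covers ongoing AEs, 7.3.1 covers significant examination findings, and the quoted sentence in 7.3.4 covers ECG abnormalities only. Requiring a Medical History entry does not forbid an AE entry. SAP 11 defines a listing and is not an instruction to sites.

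Much of this stands as to intent: 8.1 is the more specific rule and probably the intended one. But the pointer in 7.3 is general. It neither withdraws the mandatory wording of 7.3.1 nor makes an exception to it, and 8.1.1 gives a site a further reason to leave the event off the AE page. The limit on 7.3.4 is accepted in full.

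A reader might go further and infer that AE counts turn generally on the page a site chose, or that each later worsening is counted at one site and lost at another. The documents do not support that. Protocol 7.3.1 itself sends worsened findings to the AE page, and SAP 15.1 gives rows A and C the same status by both routes. Nor do events filed as medical history vanish: they are still listed, and an unchanged one would not be in the SAP 15.1 summaries anyway.

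**Conclusion.** The conflict is real, with limited consequences. The certain effect is that sites can differ on whether an ongoing parent-study toxicity enters the AE dataset and AE listing.

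An effect on summarized TEAE counts arises in two situations. One is that the parent-study date in Appendix 2 is applied (rows A and B). That date conflicts with SAP 15.1 in its own right, and it is a larger influence on the count than the routing. SAP 15.1 refers to Appendix 2 for partial dates, but the algorithm also has rows for known dates, so a programmer could apply it to every record. The other is a grade rise before rollover that triggers the might-have-worsened rule (row B), if parent grades are carried over.

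The number of patients affected cannot be derived from the documents; the 20, 10 and 5 points are illustrations per affected patient. The eCRF completion guidance is not in the documents and may already settle the routing.

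**What to change.** 1. In Protocol 7.3.1, the ECG paragraph of 7.3.4 and SAP 11, state that an AE with onset on or after the first parent-study dose and ongoing at rollover consent is recorded on the AE page under 8.1 and not as Medical History. Name the AE page in 8.1 and give the same onset limit there.
2. Keep conditions that resolved before rollover consent in Medical History, so that a toxicity that arose and ended in the parent study does not drop off both pages.
3. For carried-over AEs, define the initial grade as the grade at rollover entry. For this to work, the most extreme grade must be the worst grade from that point on; otherwise a parent-study peak still looks like worsening.
4. Align the Appendix 2 reference date for TEAEs with SAP 15.1, and add a worsening step. Row C shows that changing the date alone would drop events that worsen in rollover. The worked example at the end of SAP 15.1 also uses the first parent-study dose and should be aligned.
5. Before database lock, query Medical History entries that began after the first parent-study dose and are still ongoing.

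The cost is small: wording in the protocol, SAP and eCRF completion guideline, a small change to the TEAE derivation, and one data-management check.

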### 7.3.2 Vital Signs

Vital signs (body temperature, pulse rate, respiratory rate, and blood pressure) must be performed before dosing, and after the IMCgp100 administration (at least twice after administration) as indicated in [Table 7-1](#), and as per institutional standards. Clinically significant abnormalities are to be reported on the AE eCRF page.

Vital signs should be assessed on the scheduled day, even if study treatment is being withheld. More frequent examinations may be performed at the discretion of the investigator if medically indicated.

Frequent vital signs, as per institutional standard, should be implemented during any inpatient observations at a minimum of every 4 hours. If the full 21-day screening period is utilized for a patient, and the patient has a gap of greater than 21 days between their last dose of IMCgp100 on the parent study, and the first dose of IMCgp100 on the rollover study, the first dose of IMCgp100 (RC1D1) must be administered with overnight inpatient monitoring.

Patients experiencing a grade 3 or 4 hypotension event during any dose of IMCgp100 will require inpatient hospitalization for the next 2 doses. Further inpatient hospitalizations are at the discretion of the investigator.

Patients receiving IMCgp100 as an outpatient, for whom no grade 3 or 4 hypotension event was observed, should be monitored in the clinic for a minimum of 1 hour after the IMCgp100 infusion with at least 2 post-dose vital signs measurements performed.

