### 3.2 Definition of Study Periods

The **Screening Period** will begin once a patient has signed the consent form and concludes with either a screen failure decision or initiation of study dosing on Rollover C1D1 (RC1D1). During the Screening

Period, patients are evaluated against the study inclusion and exclusion criteria (see [Section 5](#) Population Selection Criteria). The screening window for all procedures will be up to 21 days. Please note, if the last dose of IMCgp100 on the parent study and the first dose of IMCgp100 on the rollover study are separated by more than 21 days, the first dose of IMCgp100 must be administered with overnight inpatient monitoring; given the risk of severe infusion-related toxicity and potential for hypotension (refer to [Section 1.4](#) for details of clinical experience with IMCgp100).

The **Treatment Period** will begin with the first treatment in the first cycle with RC1D1. For the purpose of treatment scheduling, a cycle consists of 4 weeks. The Treatment Period consists of the time from RC1D1 until the end of study treatment.

The **90-day Safety Follow-up Period** consists of the time from the last dose of study medication for a period of 90 days. Safety observations during this 90-day Follow-up Period are outlined in [Section 7.2.3](#) and include reporting of all AEs and all serious AEs (SAEs) in the same manner as the Treatment Period.

The **Survival Follow-up Period** will initiate after the 90-day Follow-up Period and continue until death. As applicable, all patients will be followed for survival until the end of the study is reached.

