**Table 7-1 Schedule of Study Assessments**

Procedure	Protocol Section	Screening Phase	Treatment Phase						Follow-up Phase			
			Rollover Cycle 1		Rollover Cycle 2		End of Treatment	90-day Safety Follow Up	Survival Follow Up			
		Screening a	Day 1 a	Day 8	Day 15	Day 22	Day 1	Day 8	Day 15	Day 22		

irRECIST = immune-related Response Evaluation Criteria in Solid Tumors.
 
a. Screening and Rollover Cycle 1 Day 1 (RC1D1) may be the same day, no procedures or events need to be repeated.
 
b. At Screening (or RC1D1), prior to IMCgp100 infusion, a complete physical examination will be performed. From RC1D8 onwards, a short physical examination will be performed. See Section 7.3.1.
 
c. Frequent vital signs, as per institutional standard, should be implemented during any required inpatient observations at a minimum of every 4 hours. (Refer to Section 7.3.2 for additional details).
 
d. Hematology panel should be obtained at Screening, before every IMCgp100 dose, and at the End of Treatment visit as well.
 
e. Chemistry panel should be obtained at Screening, before every dose of IMCgp100, and at the End of Treatment visit.
 
f. Cytokine panel should be obtained in all patients with a suspected occurrence of cytokine release syndrome. See Section 7.3.4.
 
g. Pregnancy testing is required in all females of childbearing potential. At Screening, a serum pregnancy test must be performed within 72 hours before the first dose of IMCgp100. During the study (Day 1 of each cycle starting with Cycle 2) a serum or urine pregnancy test must be performed. At End of Treatment, a serum or urine pregnancy test must also be performed.
 
h. Please refer to Section 6.1 Study Treatment for details of weekly IMCgp100 administration.
 
i. Immunogenicity samples are to be taken at Day 1 of all odd-numbered cycles and at End of Treatment. All samples are to be collected immediately before IMCgp100 infusion.
 
j. Target and non-target tumors to be assessed for radiographic disease progression by modified irRECIST criteria (refer to Section 7.3.5). Disease assessment to be performed at a minimum of 12 week intervals.
												

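### Protocol Section 7.3.2 states the overnight-monitoring rule with an extra condition that Sections 3.2 and 7.1 do not have, so some patients with a dose gap over 21 days meet one trigger and not the other

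*Protocol*

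**What the plan says.** The rule on overnight monitoring of the first rollover dose appears in three places in the protocol.

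- **Section 3.2 (Definition of Study Periods)** ties it to the interval between the last parent-study dose and the first rollover dose. If these "are separated by more than 21 days, the first dose of IMCgp100 must be administered with overnight inpatient monitoring". There is no other condition.
- **Section 7.1 (Screening Procedures and Assessments)** repeats this in the same words, again with the gap as the only condition.
- **Section 7.3.2 (Vital Signs)** begins: "If the full 21-day screening period is utilized for a patient, and the patient has a gap of greater than 21 days" between those two doses, then "the first dose of IMCgp100 (RC1D1) must be administered with overnight inpatient monitoring".

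Three further provisions determine whether the extra clause matters.

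- On the length of screening, Section 3.2 says: "The screening window for all procedures will be up to 21 days".
- The Screening Period, also in Section 3.2, "will begin once a patient has signed the consent form and concludes with either a screen failure decision or initiation of study dosing" on RC1D1. It is counted from consent, not from the last parent dose.
- Table 7-1, footnote a: "Screening and Rollover Cycle 1 Day 1 (RC1D1) may be the same day, no procedures or events need to be repeated".

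Footnote c of Table 7-1 says that frequent vital signs "should be implemented during any required inpatient observations at a minimum of every 4 hours" and refers the site to Section 7.3.2 for details.

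**The concern.** Sections 3.2 and 7.1 rest the requirement on one fact. Section 7.3.2 rests it on two, joined by *and*. If the second fact always accompanied the first, the extra clause would be harmless. If it does not, some patients are covered by two statements of the rule and not by the third.

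This is a safety rule: Sections 3.2 and 7.1 justify it by the danger of serious infusion toxicity and low blood pressure. Section 7.3.2 also contains the outpatient arrangement, which is at least 1 hour of observation in the clinic with at least two post-dose sets of vital signs. A site that took both its trigger and its observation instructions from Section 7.3.2 could give an outpatient first dose to a patient whom Sections 3.2 and 7.1 require to be monitored overnight.

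There is a reporting consequence too. SAP Section 9 plans a listing of important protocol violations. Whether an outpatient first dose after a gap over 21 days counts as a departure from protocol would depend on which section the assessor consulted.

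**Working it through.** The plan gives no figure to reproduce. The check is whether the two triggers select the same patients.

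**Notation (days)**

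- *d* = last parent-study dose to rollover consent
- *s* = length of screening, consent to RC1D1; from 0 (Table 7-1, footnote a) to 21 (Section 3.2)
- *g* = last parent-study dose to first rollover dose, so *g* = *d* + *s*

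**Triggers**

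- Sections 3.2 and 7.1: *g* > 21
- Section 7.3.2: *s* = 21 and *g* > 21

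They differ exactly where *g* > 21 and *s* < 21. Substituting *g* = *d* + *s*, in whole days, this requires *s* ≤ 20 and *d* ≥ 22 − *s*. That region is not empty: with *s* = 20 it needs only *d* ≥ 2, and with same-day screening it needs *d* ≥ 22.

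**Examples** (dates assumed, all within the protocol's limits, no parent dose after consent)

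| Case | *d* | *s* | *g* | Sections 3.2 and 7.1 | Section 7.3.2 |
|---|---|---|---|---|---|
| 25 days off drug, same-day screening | 25 | 0 | 25 | met | not met |
| Consent after three weeks, one-week screening | 21 | 7 | 28 | met | not met |
| Consent one week after last dose, 15-day screening | 7 | 15 | 22 | met | not met |
| Consent one week after last dose, 20-day screening | 7 | 20 | 27 | met | not met |
| Consent one week after last dose, full screening | 7 | 21 | 28 | met | met |
| Consent on day of last dose, full screening | 0 | 21 | 21 | not met | not met |

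The third and fourth rows show that no long hold before consent is needed. One weekly interval before consent, followed by screening of 15 to 20 days, is enough.

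The last row shows that full screening does not imply a gap over 21 days. The same holds if parent dosing continues after consent; Section 7.1.1.1 allows for a patient still being enrolled in the parent study during screening. Neither condition implies the other, so the clause in Section 7.3.2 narrows the trigger and does not merely restate it.

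**The case against.** The strongest reply is that the passages do not conflict logically. Section 7.3.2 says *if*, not *only if*. It describes a subset of the patients covered by Sections 3.2 and 7.1, attaches the same consequence, and exempts nobody. A site that monitors every patient with a gap over 21 days satisfies all three sections. The single-condition rule appears twice, in the sections a site would use to bring a patient to first dose, with its reason. Footnote c presupposes that the need for an inpatient stay is already settled, and the 1-hour observation applies to patients already classed as outpatients.

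This is correct as logic, and it limits the claim: Section 7.3.2 is silent on these patients and does not release them. But it relies on the site reading all three sections together. A rule that names two conditions invites the reader to treat both as necessary, and Section 7.3.2 is a natural place to look for instructions about the dosing day.

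A second reply is rarity. Inclusion criterion 1 requires active treatment, and on a weekly schedule a gap over 21 days means several missed doses. Such patients may well be few. Still, the protocol itself provides for these gaps in three places, and the examples show that screening time alone can supply most of the interval.

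A third is that Section 6.1 is partly redacted and may restate a trigger. That cannot be checked. The mismatch among the three visible passages does not depend on it.

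**Conclusion.** The concern holds. Section 7.3.2 states a narrower trigger than Sections 3.2 and 7.1 for the same requirement, and the protocol's own screening provisions make the difference real. It affects every patient whose gap exceeds 21 days and whose screening was shorter than 21 days. The documents give no information from which to estimate how many that is.

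The conclusion rests on reading full use of the screening period as 21 days from consent to RC1D1, and on the visible text only. The practical harm, an outpatient first dose where two sections require overnight monitoring, is a possibility for a site relying on Section 7.3.2 alone; it is not something the protocol directs. This is an internal inconsistency in a safety rule and should be corrected. No view is taken here on which trigger is clinically right.

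**What to change.** Reconcile Sections 3.2, 7.1 and 7.3.2 so that all three carry one identically worded trigger for overnight monitoring of the first rollover dose. Alternatively, state it once and have the other two sections refer to it. The sponsor's clinical team decides which wording stands. The unredacted Section 6.1 should be checked for a further statement of the rule and aligned if there is one.

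The cost is about one sentence of protocol text. No analysis, sample size or data collection changes.
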